## SCHEMA

## 1. BACKGROUND AND RATIONALE

### 1.1. Biochemically Recurrent Prostate Cancer

Prostate cancer (PCa) is the second most frequently diagnosed cancer and fifth most common cause of cancer death among men, causing an estimated 300,000 deaths worldwide in 2012. Although localized PCa is highly treatable with radical prostatectomy (RP) or radiation therapy (RT), approximately 20-40% of patients undergoing RP and 30-50% of patients undergoing RT will develop a biochemical recurrence (BCR) manifested as rising prostate-specific antigen (PSA) within 10 years. Despite salvage RT, many patients will continue to experience BCR. For BCR, no clear standard of care exists. The role and timing of androgen deprivation therapy (ADT) is controversial but is often considered for patients with high risk of developing metastatic disease (mPCa), especially those with PSA doubling times (PSADT) of less than 3-9 months, despite absence of strong data to support improved outcomes. In two observational studies, there was no statistically significant survival benefit conferred by use of ADT for BCR compared with delaying ADT until metastatic disease. The TOAD trial attempted to randomize patients between early ADT versus ADT at progression and did demonstrate some improvement in overall survival with early ADT, but it was significantly underenrolled and too underpowered given the small number of events to make any definitive conclusions. NCT00439751 is an ongoing trial also investigating this question. There are clear downsides to early ADT. Use of ADT in this setting may merely prolong ADT-related toxicities, including fatigue, hot flashes, weight gain, muscle loss, bone thinning, and loss of libido, thereby worsening quality of life without any downstream improvement in survival or quality of life, and therefore many patients are understandably reluctant to begin ADT in this setting. Treatment intensification with early use of docetaxel or abiraterone acetate (prior to castration resistance) is under investigation in this population in the STAMPEDE trial, but as of 2018, too few events have occurred in patients with high-risk BCR to change current practice. Alternatively, patients may be monitored until development of symptomatic or radiographic mPCa. Importantly for the design of this study, patients with clearly rising PSA and especially those with high-risk PSADTs are not expected to have spontaneous stabilization of PSA values. In addition, given the PSADT required for entry in this trial, variation in the PSA assay itself would not be expected to result in a stable PSA at the 12-week endpoint used in this trial (see Primary Endpoint, Section 2.2.1).

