### **2.1.2. Secondary Objectives**

- Determine the maximal change (proportional) and best decline (absolute) in prostate specific antigen (PSA) during nivolumab treatment
- Describe the change in PSA doubling time (PSADT) during nivolumab therapy relative to baseline
- Determine the time to development of overt metastatic disease after treatment with nivolumab
- Determine the time to initiation of androgen deprivation therapy (ADT) after treatment with nivolumab
- Assess the toxicity of nivolumab monotherapy in patients with BCR PCa

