### **2.2.2. Secondary Endpoints**

- Maximal change in prostate specific antigen (PSA) during nivolumab treatment, as a percentage of baseline
- Best PSA response during nivolumab treatment, as an absolute change relative to baseline
- Change in PSA doubling time (PSADT) at end-of-study relative to baseline
- Time from enrollment to PSA progression (10% or greater increase in PSA relative to baseline)
- Time from enrollment to development of radiographic metastatic disease
- Time from enrollment to initiation of ADT
- Safety of nivolumab

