## 6.7. Protocol Therapy Discontinuation

In addition to discontinuation from therapy related to toxicities as outlined above, a subject will also be discontinued from protocol therapy and followed per protocol under the following circumstances outlined below. The reason for discontinuation of protocol therapy will be documented on the electronic case report form (eCRF).

The Prostate Cancer Working Group 3 (PCWG3) recognizes that favorable effect of experimental therapies on PSA may be delayed for  $\geq 12$  weeks and recommends continuing treatment through early rises for a minimum of 12 weeks unless there is other evidence of progression.

PCWG3 recommends continuing experimental therapies for subjects who experience PSA rise after initial decline, in the absence of any radiographic or clinical progression. However, subjects in this trial do have access to a standard-of-care treatment in the form of ADT which can be used to delay development of metastatic disease, although a convincing survival benefit has not been established in this setting. This trial requires treatment discontinuation only for the reasons below, but investigators are advised to use discretion for patients with rapidly increasing PSAs (after 12 weeks of treatment). Patients believed to be clinically benefitting, for example based on decreased PSADT after starting nivolumab, could be continued on treatment at the investigator's discretion.

- Documented metastases on imaging (see Section 9 for definitions).
- Completed 2 years of treatment with nivolumab
- Site investigator determines a change of therapy (i.e. starting ADT) would be in the best interest of the subject
- Subject or legal representative (such as a parent or legal guardian) withdraws consent and requests to discontinue protocol therapy, whether due to unacceptable toxicity or for other reasons
  - In a subject decides to prematurely discontinue protocol therapy (“refuses treatment”), the subject should be asked if he or she may still be contacted for further

scheduled study assessments. The outcome of that discussion should be documented in both the medical records and in the eCRF.

- Unacceptable adverse experiences
- Intercurrent illness that prevents further administration of treatment
- Protocol therapy is interrupted for > 6 weeks (calculated from the date of the first missed dose). Any potential exceptions to this criteria must be discussed with and approved by the PI.

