## 7. STUDY CALENDAR & EVALUATIONS

Event	Screening	On Treatment (28-day cycles)	End of Study i	Follow-Up
	≤ 28 days prior to enrollment	Day 1 j	Within 30 days of last dose	Every 3 months until mPCa
Informed consent	X			
Confirmation of all eligibility criteria	X k			
Medical history a	X		X	X l
Prior systemic and radiation therapy b	X			
Physical examination c	X	X	X	
ECOG performance status	X	X	X	
Concomitant medication review	X	X	X	
Adverse Event review	X	X	X	X l (100 days after last nivolumab dose)
Chemistries d	X	X		
Hematology d	X	X		
TSH (with reflex free T4 testing if abnormal)	X	X		
Prostate-specific antigen e	X	X	X	
Archival tissue testing for PD-L1 expression and NGS f	X (After tissue pre-screen consent, prior to full informed consent, for patients enrolled under AM2)			
Blood for exploratory studies g		Cycles 1 and 2; q4 cycles beyond cycle 4 (C5, C9, etc.). Optional collection 1 week after cycle 1.	X	
Radionuclide bone scan and CT of abdomen/pelvis with contrast h	X	X (Prior to cycle 4 and every 3 rd cycle thereafter)		
Nivolumab administration		X		

Abbreviations: AE=adverse event; CBC=complete blood count; ECOG=Eastern Cooperative Oncology Group (performance score); EOS=end-of-study; mPca=diagnosis of metastatic prostate cancer; NGS=next-generation sequencing (e.g. Foundation One, OncoPanel).

- a Medical history: including relevant medical history collection, as well as Gleason score and TNM stage at diagnosis, results of any recent advanced imaging (Axumin, SPECT, choline, sodium fluoride, etc.)
- b Collect radiation site, administered dose per fraction and treatment duration, as well as any concurrent ADT and duration of ADT.
- c Physical examination includes height (at screening only), weight, vital signs, and general physical examination

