- i End of study (EOS) assessments should be conducted in-person within 30 days after the last dose of nivolumab. AEs will also be assessed at 100 days after the last dose of nivolumab in the Follow-up Period (see footnote l). Patients must contact the study team regarding any significant toxicities or illnesses that occur within 100 days of last nivolumab dose, as SAEs must be reported during this time. For patients experiencing toxicities, EOS visits should occur every 2 weeks ( $\pm$  3 days) until toxicities resolve. Depending upon the toxicity, the every 2-week assessment may be accomplished via phone call, email or other avenues as appropriate. Mode of assessment will be at site investigator's discretion.
- j All visits have a window of  $\pm$  3 days.
- k Baseline imaging may be performed up to 60 days prior to enrollment.
- l Follow-up period will continue until documentation of metastatic disease (via radiographic imaging and/or biopsies). Follow-up may consist of medical record review (for patients treated at BIDMC) or contact via phone/email (for patients treated at non-BIDMC institutions). Data to be collected includes: date of initiation of any subsequent hormonal therapy, date of documented metastatic disease, and any other therapies received during follow-up period. If contact is made via phone/email with patient, then written documentation must be provided to confirm these dates and the diagnosis of metastatic disease. In addition, the research nurse must attempt to contact the patient (via phone or email depending on patient preference) approximately 100 days after the

last dose of nivolumab, +/- 1 week, to assess AEs. If the patient cannot be reached, attempts should be documented in the medical record and this will not be considered a deviation from protocol.

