#### **12.2.2. Secondary analysis and analysis of safety**

Maximum PSA change and best PSA response will be summarized descriptively and graphically in waterfall plots. PSA doubling time will be calculated with linear regression model of natural logarithm of PSA and time. PSADT at baseline and

EOS will be summarized, and change in PSADT, as captured by the change in PSA slope, will be summarized descriptively as well. Time to event endpoints will be summarized using Kaplan Meier estimate.

All reported toxicities, regardless of attribution, will be summarized by toxicity type and maximum grade. The maximum grade consolidates the reports of a given toxicity for a patient over time by taking the maximum across time. Immune modulatory medication used for toxicities will also be summarized descriptively.

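### Follow-up is written to end at documented metastasis, but time to ADT is not limited to ADT before metastasis and has no censoring rule, so its Kaplan-Meier curve is likely biased upward

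*Combined protocol and SAP*

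**What the plan says.** - **Objective and endpoint.** Section 2.1.2 sets the aim: "Determine the time to initiation of androgen deprivation therapy (ADT) after treatment with nivolumab". Section 2.2.2 gives the endpoint as "Time from enrollment to initiation of ADT". Neither restricts it to ADT begun before metastasis.
- **Length of follow-up.** The Follow-Up column of the section 7 calendar reads "Every 3 months until mPCa". Footnote l repeats the stopping point: "Follow-up period will continue until documentation of metastatic disease (via radiographic imaging and/or biopsies".
- **Data collected.** Footnote l lists "date of initiation of any subsequent hormonal therapy, date of documented metastatic disease, and any other therapies received during follow-up period". Record review or phone/email contact is allowed.
- **Analysis.** Section 12.2.2 says "Time to event endpoints will be summarized using Kaplan Meier estimate". It gives no rule for censoring or competing events.
- **Clinical setting.** Section 1.1 discusses delaying ADT until metastatic disease and adds: "Alternatively, patients may be monitored until development of symptomatic or radiographic mPCa". Section 6.7 lists among the reasons to end protocol therapy "Documented metastases on imaging (see Section 9 for definitions".

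**The concern.** The stopping point suits the time-to-metastasis endpoint but was not matched to the ADT endpoint. In a man who has deferred ADT, metastasis is a natural trigger for starting it, and that is where planned data collection closes. Kaplan-Meier treats a man who leaves follow-up as having the same future ADT risk as those still followed. For these men the risk is probably higher, so the ADT-free curve is pushed up.

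Section 1.9 asks whether the strategy can delay the need to start ADT, as groundwork for a larger trial. With a single arm, no control group shares the bias, and a date not collected at the time may be hard to recover at analysis.

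**Working it through.** **The plan's own figures.** None is stated for time to ADT. The section 12.1 figures concern 12-week disease control and reproduce by exact binomial calculation: at least 2 of 20 gives alpha 0.017 and power 97.6% (stated 0.02 and 97%), and at least 1 of 14 gives 0.131 and 95.6% (stated 0.13 and 96%). They are not affected.

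**What would be captured.**
1. ADT before metastasis: captured.
2. Metastasis on a scheduled on-treatment scan: imaging may be done up to 8 days before the next day 1 of a 28-day cycle, so about day 20 to 28 after the last dose. The end-of-study visit falls within 30 days of that dose. On schedule this leaves 30 − 28 = 2 to 30 − 20 = 10 days for ADT to start and be noted. The 100-day contact is specified for adverse events only.
3. Metastasis after treatment: ADT is captured if it has begun by the contact at which the metastasis is learned. No later contact is planned.

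**Assumptions (none in the documents).** Constant hazards; a 12-month median to first event (ADT or metastasis), so λ = ln 2/12 per month; q = share of first events that are metastasis; ADT a fixed lag L after metastasis.

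**Formulas.**
- Strict reading (nothing captured after metastasis): Kaplan-Meier estimates exp(−λ(1−q)t). Its median is 12/(1−q), and its two-year value is 0.25^(1−q).
- True curve for t > L: exp(−λt) × [(1−q) + q·2^(L/12)]. Its median is 12 + ln[(1−q) + q·2^(L/12)]/λ. Example, q = 0.5 and L = 1: 12 + ln(1.0297)/0.05776 = 12.5.
- Lenient reading (the next 3-monthly contact captures ADT already begun): by simulation. With L = 1 month about 69% of post-metastasis starts are captured, close to (3−1)/3.

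**Median time to ADT in months, L = 1 month**

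| q | True | Strict | Lenient |
|---|---|---|---|
| 5% | 12.05 | 12.6 | 12.2 |
| 10% | 12.1 | 13.3 | 12.5 |
| 20% | 12.2 | 15.0 | 13.0 |
| 30% | 12.3 | 17.1 | 13.5 |
| 50% | 12.5 | 24.0 | 14.5 |

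Two-year ADT-free rates for q = 20%, 30% and 50% are 33%, 38% and 50% (strict) and about 27%, 29% and 31–32% (lenient), against a true 25–26%.

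**Effect of the lag.** With a fixed 3-month lag, no ADT start falls before the next 3-monthly contact. The lenient medians for q = 20%, 30% and 50% become about 15, 17 to 18 and 24 to 25 months, close to the strict ones, against true medians of 12.6, 13.0 and 13.6.

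**Other hazards.** A second simulation took medians of 12, 24 or 48 months for each of pre-metastasis ADT and metastasis, with an exponential lag of mean 1 or 3 months. The strict median exceeded the true one in all 18 combinations, and so did the lenient one. With both medians at 24 months and a 1-month mean lag, they were 24.0 (strict), 14.4 (lenient) and 12.5 (true). With a 3-month mean lag they were 24.1, 18.0 and 13.7.

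**The case against.** A reader might infer that ADT after metastasis is never recorded. The documents do not support that. Footnote l collects dates of subsequent hormonal therapy. Protocol imaging stops at end of study, so later metastases come to light in usual care and reach the trial at the next contact, by which time ADT may have begun. Section 9.1 requires new bone lesions to be confirmed on the next scan and back-dates progression, so documentation can trail the metastasis date. This stands, and it is why the lenient column is shown. It gives little help for metastasis found on treatment, or when the lag is long.

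A reader might also infer that the plan prescribes censoring at metastasis. It does not: that is the natural result of ending follow-up there and applying plain Kaplan-Meier, but section 12.2.2 is silent.

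The share q could be small. Section 1.1 says ADT is often considered when PSA doubling time is under 3 to 9 months, entry requires under 10 months, and section 6.7 names starting ADT as a reason to stop nivolumab. At q = 5% to 10% even the strict median is only 12.6 to 13.3 months. Against this, section 1.1 notes that many patients are reluctant to begin ADT, and exclusion 1 removes men who plan to start it during the trial. The documents do not settle q.

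Finally, the endpoint is descriptive, with no test or threshold, and time to metastasis is reported alongside. That limits the consequence but does not correct the curve.

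**Conclusion.** The mismatch between follow-up and endpoint is in the current text. Followed as written, the plan loses some ADT dates after metastasis, and the likely bias is toward longer ADT-free time. The direction rests on one assumption, supported by section 1.1: men who reach metastasis without ADT are more likely to start it soon than men still followed.

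The size cannot be fixed from the documents. Under the 12-month, 1-month-lag assumptions, the excess in the median runs from 0.2 month (12.2 against 12.05; q = 5%, lenient) to 11.5 months (24.0 against 12.5; q = 50%, strict). The strict figures are an upper reading for each q and should not be quoted alone as the effect of the plan. The primary endpoint, the success rules and the sample size are untouched. The change is worth making because it is cheap and the missing dates may not be recoverable later.

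**What to change.** 1. In the Follow-Up header and footnote l, continue record review or phone/email contact every 3 months until both metastatic disease and the start of ADT are documented, or until death, withdrawal or study close.
2. In section 12.2.2, state that time to ADT is not censored at metastasis, and give the censoring rule.
3. If ADT dates after metastasis cannot be collected, choose one alternative and apply it to every patient: time to the first of ADT or metastasis, or cumulative incidence of ADT with metastasis as a competing event. Either answers a different question from the present endpoint and should be labelled so. Do not count metastasis as the event only for men whose ADT date is missing, since that mixes two endpoints in one curve.

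The cost is the wording change plus one or a few extra record reviews or contacts for each man who metastasises before ADT. Footnote l already allows these methods. No visit or procedure is added, and patient management does not change.

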## 8. BIOSPECIMEN STUDIES AND PROCEDURES

As discussed above, early trials of PD-1/PD-L1 blockade showed a disappointing efficacy in castration-resistant prostate cancer (CRPC). The failure of PD-1/PD-L1 checkpoint blockade in CRPC has been hypothesized to be due to poor immunogenicity of PCa and subsequently lack of immune resistance in PCa, supported by absence or little PD-L1 expression on prostate cancer cells. However, recently there have been a number of reports describing significant PD-L1 positivity in both primary PCa (up to 61.7%) and CRPC (up to 19%), presumably due to improvement of antibody and immunostaining sensitivity. In clinical practice, it is not uncommon to encounter primary PCas that are enriched in TILs. Therefore, we have hypothesized that a subset of PCas are immunogenic and upregulate immune checkpoint molecules such as PD-L1. Identification of this fraction of “hot” PCas may correlate with response to immune checkpoint inhibition, a hypothesis we will test in this trial.

Third, we will consider exploratory analyses of tumor neoantigens and peripheral T-cell reactivity. Whole-exome sequencing (WES) of primary tissue may be used to identify potential tumor neoantigens that could be the target of effector T-cell responses. Sequential peripheral blood collections will allow banking of antigen-presenting cells and T-cells. If there are patients with strong responses to nivolumab treatment, we will consider evaluating their banked samples for evidence of T-cell responsiveness to the potential neoantigens identified in the patients' primary tumor WES data.

Fourth, banked blood would allow future analysis of circulating tumor DNA to investigate whether mutations in the primary tissue correlated with mutations at the time of biochemical recurrence.

Finally, we will assess changes in soluble biomarkers (cytokines, chemokines) during treatment, which may correlate with treatment response.

## **8.2. Tissue Collections**

### **8.2.1. Archival Tumor Tissue**

Archival tumor tissue will be requested prior to registration. For patients who underwent primary prostatectomy, prostatectomy slides and blocks will be obtained. For patients who underwent primary radiation therapy, diagnostic core-needle biopsy slides and tissue blocks will be obtained. Slides will be reviewed at BIDMC. For each patient, one to two tissue blocks that contain the greatest dimension of tumor will be used for screening and exploratory studies (please see Section 5.1); the remainder may be used for exploratory studies.

### **8.2.2. Peripheral Blood**

Blood will be collected as outlined in the study calendar (section 7). Please see appendix 3 for details of tubes, volume, and delivery.

## **8.3. Storage of Biospecimens**

All specimens not exhausted in planned exploratory studies for this trial will be stored for future research.

## **8.4. Confidentiality of Biospecimens**

All samples will be labeled with the following identifier system:

- Patient's enrollment number
- Patient's initials

- Protocol number
- Collection timepoint (cycle number)  
Example: 01-AB-18XXX-1

Any material issued to collaborating researchers will be anonymized and only identified by this identifier.

## 8.5. Collection and Shipping of Research Blood Samples

For patients enrolled at non-BIDMC sites, research tubes as described above will be drawn as per the study calendar. To arrange pick-up, a BIDMC clinical research assistant should be contacted by email ([[contact]](mailto:[contact])) with the subject line including protocol number and “Blood Collection.” Blood samples for germline WES will be brought to the [name] lab at Center for Life Sciences, 4th Floor, [name]. Blood samples for T-cell isolation and banking will be brought to the [name]/[name] lab, also at Center for Life Sciences, on the 6th floor and under the care of [name] (contact [[contact]](mailto:[contact]) in advance to arrange delivery).

## 9. CRITERIA FOR DISEASE EVALUATION

As per the Prostate Cancer Working Group 3 (PCWG3), a rising PSA is typically the first sign of tumor regrowth, followed later by worsening of disease by imaging and the development of clinical symptoms. Since there may be some interassay variability, subjects should have PSAs measured while on study at a single institution. PSAs from other institutions prior to enrollment are acceptable with the caveat that clear rise must be demonstrated and that interassay variability should be factored into this assessment. For this study, we are using the PCWG3-designated “control/relieve/eliminate” endpoints for therapies expected to be cytotoxic. In limited experience with MSI-high PCa that responds to PD-1 blockade, PSAs have fallen dramatically. It is also possible that stabilization of PSA will be a clinically meaningful endpoint if it delays or prevents development of metastatic disease and/or need for ADT; therefore, PSA stabilization is included in the primary endpoint.

